Part C (Cohorts 6 and 7): 19 doses of LY3002813 or placebo administered Q4W for 72 weeks followed by 12-weeks follow-up

Criteria for Evaluation:

Safety: Safety parameters that will be assessed include AEs, concomitant medications, cognitive function, physical and neurological examinations, vital signs, electrocardiogram, safety laboratory values, and MRI scans.

Bioanalytical: Serum and CSF samples will be used to determine concentrations of LY3002813. Serum and CSF concentrations of LY3002813 will be determined by validated enzyme-linked immunosorbent assay.

Pharmacogenomics: A blood sample will be used to test for genetic variants that may influence response to treatment.

Pharmacokinetic/Pharmacodynamic: Blood and CSF samples will be used to determine the concentrations of LY3002813. Cortical standardized uptake value ratio (SUVr) from florbetapir and 18F-AV-1451 positron emission tomography scans will be analyzed to estimate mean change. The CSF results from the lumbar punctures taken pre- and postinfusion will be analyzed to estimate the mean change from preinfusion. The dependent variables are $\text{A}\beta_{1-40}$, $\text{A}\beta_{1-42}$, total tau, and phospho-tau.

Statistical Evaluation Methods:

Up to approximately 150 patients may be enrolled to ensure that a minimum of approximately 72 patients complete the study. The sample size is customary for studies evaluating safety, PK, and/or PD parameters; at the conclusion of the trial, confidence intervals for PK, PD, and cognition endpoints may be computed in order to evaluate the precision of the estimates where appropriate. In addition, based on prior Lilly clinical trials, 6 patients randomized to each LY3002813 dose and placebo provide over 90% power to detect at least a 17% mean florbetapir SUVr reduction of a dose compared to placebo without multiple comparison adjustment.

Statistical: PK/PD analyses will be conducted on the full analysis set. This set includes all data from all randomized patients receiving at least 1 dose of the investigational product according to the treatment the patients actually received. Safety analyses will be conducted for all enrolled patients, whether or not they complete all protocol requirements. A model-based approach of analysis will be used. Summary statistics, data tabulations, and data graphs by ethnicity (Japanese and non-Japanese) will be provided as appropriate.

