Cohort 2 will only be initiated after review of safety data from Cohort 1. Thereafter, Cohort 3 will be initiated after review of safety data from Cohort 2. Cohorts 4 and 5 will be initiated after review of safety and PK data from their respective single-dose cohorts. An additional requirement for Cohort 5 is confirmation that at least 2 patients have received at least 3 doses each of LY3002813 safely in Cohort 4. Cohort 6 and Cohort 7 may proceed in parallel with Cohorts 4 and 5, respectively. In addition, Cohort 7 will only be initiated after confirmation that at least 2 patients have received at least 2 doses each of LY3002813 safely in Cohort 6.

Safety/PK reviews will occur after a minimum of 4 patients receiving LY3002813 and 1 patient receiving placebo have been dosed. For Cohorts 1 to 3, no more than 1 patient will be dosed on any one particular day. For Cohorts 4 to 7, patients dosed on the same day at any one site should not be dosed simultaneously but should be separated by at least 1 hour. Each cohort will contain approximately 6 (single dose) or 9 (multiple dose) patients treated with LY3002813 and 2 to 3 patients treated with placebo so that the study can detect target engagement and ADA frequency relative to those observed in Study AACC.

The primary target engagement outcome is the reduction of cerebral amyloid as measured by quantitative amyloid PET imaging (florbetapir SUV_r) assessed at baseline and at 12 weeks, 24 weeks, 36 weeks, 48 weeks, and 72 weeks after starting treatment. The early postbaseline scans are aimed to assess the time course of amyloid reduction; the later scans are aimed to assess sustainability of amyloid reduction after completion of dosing in Parts A and B, and maximal amyloid removal in Part C.

Safety and PK of LY3002813 will be assessed throughout the study for each cohort. In addition, blood samples for the assessment of immunogenicity will be taken at regular intervals throughout the dosing and follow-up periods. For Cohorts 1 through 3, a CSF sample will be taken by single lumbar puncture (LP) at baseline, another approximately 3 days after dosing to measure the CSF concentration of LY3002813 and CSF biomarkers. For Cohorts 4 through 7, a CSF sample will be taken by single LP at baseline and after 24 weeks dosing, or the last dose if treatment is stopped earlier.

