7.1.5. Part C: Chronic, 72-Week Q4W Multiple Dose Cohorts (Cohorts 6 and 7)

Safety, PK, and PD will be assessed in Cohorts 6 and 7 during and after multiple doses of LY3002813 or placebo have been administered Q4W for up to 72 weeks, or when the LY3002813-induced reduction in amyloid measured by florbetapir reaches the maximum reduction (defined as SUVr <1.1 for 2 consecutive scans) (Joshi et al. 2015). The planned doses are 10 and 20 mg/kg IV with 12 patients (9 LY3002813; 3 placebo) planned to be enrolled in each cohort. Cohort 6 (10 mg/kg IV Q4W) and Cohort 7 (20 mg/kg IV Q4W) may proceed, in parallel with Cohorts 4 and 5, respectively. In addition, Cohort 7 will only be initiated after confirmation that at least 2 patients have received at least 2 doses each of LY3002813 safely in Cohort 6. The maximum dose of 20 mg/kg will not be exceeded. If a patient is deemed to be amyloid negative by florbetapir PET before completion of 18 months' dosing (SUVr <1.1 for 2 consecutive scans), the patient will receive placebo infusion for all subsequent visits and continue the Part C visit schedule, including assessment of sustained amyloid reduction at the scheduled PET scan assessments. Safety, PK, and PD will be assessed for all patients at regular intervals for approximately 12 weeks after completion of 72 weeks of dosing with LY3002813 ([Attachment 1](#)).

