11.1. Determination of Sample Size

Up to approximately 150 patients may be enrolled so that approximately 72 patients complete the study. Cohorts 1, 2, and 3 are each planned to have approximately 8 patients (6 LY3002813; 2 placebo) complete the study. Cohorts 4 and 5 are each planned to have approximately 12 patients (9 LY3002813; 3 placebo) complete the study. Also, Cohorts 6 and 7 are each planned to have approximately 12 patients (9 LY3002813; 3 placebo) complete the study.

The sample size is customary for studies evaluating safety, PK, and/or PD parameters; at the conclusion of the trial, confidence intervals for PK, PD, and cognition endpoints may be computed in order to evaluate the precision of the estimates where appropriate. Based on prior Lilly clinical trials, 6 patients randomized to each LY3002813 dose and placebo provide over 90% power to detect at least a **CCI** mean SUV_r reduction of a dose compared to that of placebo without multiple comparison adjustment. Based on Fixed and Adaptive Clinical Trial Simulator simulations, there is over 90% success rate that at least 1 LY3002813 dose separates from placebo with a success criterion of $\Pr(\text{mean SUV}_r \text{ reduction of LY3002813 dose} < \text{mean SUV}_r \text{ reduction of placebo}) > \text{CCI}$. If more patients are needed to determine safety, target engagement, PK, dosing, and/or race differences, then up to a total of 10 additional patients may be added.

Patients who are randomized but who do not complete the 12-week safety and PET assessments may be replaced.

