- r Predose and end of infusion samples should be collected. The “predose” collection indicates that the sample should be taken up to 30 minutes before the beginning of the infusion. The “end of infusion” collection indicates that the sample should be taken as close to the completion of the infusion as possible. Postdose samples should be collected from a different arm than was used to administer study drug.

- s If the immunogenicity titer at the last scheduled assessment or discontinuation visit is positive, then additional safety assessments (concomitant medications, AEs, safety laboratory values, ECGs, vital signs) and samples for immunogenicity and PK should be taken every 12 weeks until the titer returns to baseline (comes within a single 2-fold dilution of the baseline titer), or up to 48 weeks after the last dose of LY3002813 if the antibody titer has not returned to baseline within 48 weeks after the last dose. In the case of a patient whose result is positive at baseline with a 1:10 titer and subsequently develops a treatment-emergent ADA response that increases to much higher titers, the antibody titer would need to decline to a titer of 1:20 or less to be considered a “return to baseline.” In contrast, if the patient’s result is “not detected” at baseline (in an assay with a 1:10 minimal required dilution), the titer would need to decline to either “detected” with a 1:10 titer or a result of “not detected” to be considered a “return to baseline.”
- t Stored serum samples for possible immune safety laboratory testing (including but not limited to β tryptase, total Immunoglobulin E, and immune complex testing) will be collected. In the event of a moderate or severe infusion reaction event, additional unscheduled samples should be collected approximately 60-120 minutes and 4-6 weeks after moderate or severe infusion reactions. Failure to collect these samples will not qualify as a protocol violation. Unscheduled samples may also be collected as needed.
- u Performed predose and end of infusion and 2 hours after the end of infusion on dosing days.
- v Performed predose and end of infusion.
- w If a patient is deemed to be amyloid negative by florbetapir PET before completion of 18 months’ dosing (SUVr <1.1 for 2 consecutive scans), the patient will receive placebo infusion for all subsequent visits, and continue the Part C visit schedule.

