### **4.2.7. Safety Analyses**

#### **4.2.7.1. Clinical Evaluation of Safety**

All investigational product and protocol procedure AEs will be listed. At a minimum, all safety data will be summarized using descriptive methodology.

The incidence of symptoms for each IV dose will be presented by severity and by association with investigational product, as perceived by the investigator. Symptoms reported to occur before randomization will be distinguished from those reported as new or increased in severity during the study. Each symptom will be classified by the most suitable term from the medical regulatory dictionary.

The number of investigational product-related SAEs will be reported.

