#### 4.2.7.2. Statistical Evaluation of Safety

Safety parameters that will be assessed include safety clinical laboratory parameters, vital signs, and ECG parameters. The parameters will be listed and summarized using standard descriptive statistics. Additional analysis will be performed if warranted upon review of the data.

A shift table for each IV dose will be constructed to assess the MRI measurement pre- and postdose for changes and additions of vasogenic edema and microhemorrhages (ARIA-E and ARIA-H)

Suicide-related thoughts and behaviors based on the C-SSRS will be listed by patient. Only time points and patients that show ideation/behavior of suicide will be displayed (ie, all “no” responses may not be displayed).

Exploratory analyses of Fridericia's corrected QT interval (QTcF) data from ECG monitoring in a Phase 1 trial are performed to judge the extent and/or risk of QT prolongation. There will be an exploratory assessment of potential prolongation by examining mean change in QTcF as a function of serum drug concentration obtained and an inspection of the upper confidence limit relative to a value of 10 msec, which is consistent with International Conference on Harmonisation (ICH) guidance. Frequency tables of QTc changes from baseline and large QTc values may also be obtained in accordance with ICH guidance.

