#### 4.2.7.3. Evaluation of Immunogenicity (for Large Molecules)

As part of the secondary study objective, Antibody drug formation will be summarized over time for each IV dose group. An MMRM will be done fitting IV dose, study visit, and interaction between study visit and dose as fixed effects and the dependent variable as the change from baseline in antibody formulation following dosing of LY3002813. The relationship between the presence, absence or level of ADAs and number of IV drug infusion reaction AEs, PK estimates of exposure, PD measurements of amyloid SUVR. These associations may be assessed using simple pairwise correlations and pairwise graphical relationship. These relationships may also be described using a modeling approach, if appropriate.

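### Part C safety and antibody tables by IV dose take no account of the switch to placebo after amyloid clearance, so they do not give the risk of 72 weeks on drug

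*Protocol*

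**What the plan says.** Protocol 7.1.5 and footnote w of the Study Schedule (Attachment 1) set the switch. A Part C patient whose florbetapir SUVr is below 1.1 on two consecutive scans stops receiving LY3002813, and "the patient will receive placebo infusion for all subsequent visits, and continue the Part C visit schedule". The schedule collects adverse events through Visit 27 at Week 84. The Synopsis gives the full course as "19 doses of LY3002813 or placebo administered Q4W for 72 weeks followed by 12-weeks follow-up".

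The SAP organises the safety and antibody output by dose:

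- Section 4.2.7.1: "The incidence of symptoms for each IV dose will be presented by severity and by association with investigational product".
- Section 4.2.7.2, for ARIA: "A shift table for each IV dose will be constructed to assess the MRI measurement pre- and postdose".
- Section 4.2.7.3: "Antibody drug formation will be summarized over time for each IV dose group", with a repeated-measures model of change from baseline on dose, visit and their interaction.

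SAP 4.2.1 analyses the PK/PD set by treatment actually received. It says only that safety analyses cover all enrolled patients. The SAP does not mention the switch, and it specifies no on-drug period, no count of drug infusions and no exposure-adjusted rate. Analyses of exposure against adverse events or antibodies (Protocol 11.2.6, SAP 4.2.6) are optional and mainly graphical.

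**The concern.** After the switch a patient has placebo infusions and an off-drug period, but no rule says how events in that period are attributed. The natural reading of a table by dose is that they are counted under 10 or 20 mg/kg every 4 weeks. Because the switch is triggered by response, a cohort that clears amyloid faster receives fewer drug infusions over the same 84 weeks.

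The relatedness column does not separate the two kinds of infusion. The protocol's definition of investigational product includes placebo, investigators are blinded through follow-up (Attachment 4), and possibly related events count as related (Protocol 10.6.1). A reaction to a post-switch placebo infusion can therefore appear as a related event under a drug dose.

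At stake is how the Part C results are read. Protocol 5.2 makes manageable infusion-reaction risk and low ARIA incidence conditions for further development. A row labelled as chronic 72-week dosing could rest partly on patients who had about a third of the planned drug infusions.

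**Working it through.** **Inputs.** Infusions are every 4 weeks from Week 0 to Week 72. Florbetapir scans are "assessed at baseline and at 12 weeks, 24 weeks, 36 weeks, 48 weeks, and 72 weeks after starting treatment" (Protocol 7.1). The switch needs two consecutive scans below 1.1. For cohort size, "Cohorts 6 and 7 are each planned to have approximately 12 patients (9 LY3002813; 3 placebo) complete the study" (Protocol 11.1).

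**The plan's own figure.** 72/4 + 1 = 19 infusions, which reproduces the stated 19.

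**Drug infusions before a switch.** The lower count assumes the second scan is acted on before that visit's infusion, the higher count after it.

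| Qualifying scans (weeks) | LY3002813 infusions | Placebo infusions |
|---|---|---|
| 12 and 24 | 6 or 7 | 13 or 12 |
| 24 and 36 | 9 or 10 | 10 or 9 |
| 36 and 48 | 12 or 13 | 7 or 6 |
| 48 and 72 | 18 or 19 | 1 or 0 |

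**What this could do to patient incidence.** The documents give no risk per infusion, so *p* is an assumption, shown as a range. If *p* is constant and only drug infusions carry it, the chance of at least one event in *k* drug infusions is 1 − (1 − *p*)^*k*.

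| Assumed *p* | *k* = 7 | *k* = 13 | *k* = 19 |
|---|---|---|---|
| 0.5% | 3.4% | 6.3% | 9.1% |
| 1% | 6.8% | 12.2% | 17.4% |
| 2% | 13.2% | 23.1% | 31.9% |
| 5% | 30.2% | 48.7% | 62.3% |

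**Partial switching.** With *m* of 9 patients switched after 7 infusions and *p* = 1%, the row shows [*m* × 6.8% + (9 − *m*) × 17.4%]/9. That is 17.4% for *m* = 0, 13.9% for *m* = 3, 10.3% for *m* = 6 and 6.8% for *m* = 9.

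**Contrary case.** If all the risk lies in the first three infusions, at 5% each, incidence is 1 − 0.95³ = 14.3% whether a patient has 7 or 19. There is then no dilution.

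**Effect of using drug infusions as denominator.** At *p* = 1%, nine patients with 7 drug infusions each have 63 infusions and 0.63 expected reactions. Nine with 19 each have 171 infusions and 1.71 expected reactions. Both give 1% per infusion, whatever the switch time.

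**The case against.** The strongest reply is that a table by cohort is a valid summary of the regimen under test. Part C dosing is defined as up to 72 weeks or until maximum reduction, so fewer infusions at a faster-clearing dose are part of that regimen. Safety is also descriptive, with no formal test of 10 against 20 mg/kg. Both points stand. The table misleads only if it is read as the risk of 72 weeks on drug.

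The reply on timing is also substantial. In the earlier study of this antibody (Protocol 5.1), all 6 patients with infusion reactions first reacted after the first or second dose of the multiple-dose phase. More than 90% of patients with AD had treatment-emergent antibodies 3 months after the first dose. Both precede Week 24, the earliest possible switch. Early reactions and early antibody positivity would therefore be little affected. However, that phase gave at most 4 doses and had no reactions at 10 mg/kg, so it cannot show what happens over 19 infusions at 10 or 20 mg/kg. Its antibody titers also tended to rise towards the end of the phase. The SAP's antibody model is already by visit, but its late visits would mix on-drug and off-drug titers within a dose.

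For ARIA, MRI continues after the switch, so detection is not lost. The documents give no evidence of a late or cumulative ARIA hazard; it remains a possibility.

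A reader might infer two stronger things. One is that the SAP assigns post-switch events to the drug dose. It does not say so; it is silent. The other is that the 10 versus 20 mg/kg comparison is shown to be biased, so that a riskier dose would look safer. That needs assumptions from outside the documents. Take 4% per infusion at 20 mg/kg against 2% at 10 mg/kg, with nobody switching at 10 mg/kg. If 6 of 9 at 20 mg/kg switch after 7 infusions, expected incidence is [6 × 24.9% + 3 × 54.0%]/9 = 34.6%, still above 31.9%. The order reverses only from 7 of 9. If all 9 switch after 10 infusions, 33.5% is again above 31.9%.

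**Conclusion.** The gap is real and moderate. The protocol can replace up to 12 or 13 of 19 drug infusions with placebo on the basis of response, and the SAP's tables by dose neither show this nor adjust for it. As written, they describe dosing every 4 weeks until clearance. They do not give the risk of 72 weeks on drug, and they can understate late adverse events, late ARIA and late antibody titers in whichever cohort clears faster.

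The size cannot be determined, since it depends on the share of patients who switch, when they switch, and how risk is spread over infusions. It ranges from none, if risk is confined to the first few infusions or switches come only at Week 72, to the contrasts in the incidence table under a constant risk. A biased ranking of the two doses is not established.

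**What to change.** In SAP 4.2.7.1 to 4.2.7.3, state how events after the switch are attributed. For Cohorts 6 and 7, keep the whole-study tables by dose and add:

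- (a) for each dose, the number of patients switched and the number of LY3002813 infusions received;
- (b) infusion reactions per LY3002813 infusion, with reactions on post-switch placebo infusions shown separately;
- (c) adverse-event, ARIA and antibody summaries split at the patient's last LY3002813 infusion plus a stated follow-up window, for example the 12 weeks the protocol uses after Part C dosing.

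Show time at risk beside the counts in (c), because a shorter on-drug period lowers the crude percentage even after the split. The post-switch period consists of responders only, so it should be read descriptively.

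The dates are available in principle: dose administration times are recorded (Protocol 9.2), and extended antibody follow-up is already tied to the last dose of LY3002813 (Protocol 10.4.1). The cost is SAP wording, some programming and sparser cells with 9 treated patients per cohort. No change to the clinical switch rule is proposed.

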Attachment 2. Protocol AACD Clinical Laboratory Tests

Laboratory Tests at Screening (Performed at Local Laboratory)

Hematology	Clinical chemistry
Hematocrit	Sodium
Hemoglobin	Potassium
Erythrocyte count (RBC)	Bicarbonated ^d
Mean cell volume	Chloride
Mean cell hemoglobin	Calcium
Mean cell hemoglobin concentration	Glucose (random)
Leukocytes (WBC)	Blood urea nitrogen
Cell morphology (absolute or relative % counts)	Total protein
Neutrophils	Albumin
Lymphocytes	Total bilirubin
Monocytes	Alkaline phosphatase
Eosinophils	Aspartate aminotransferase (SGOT)
Basophils	Alanine aminotransferase (SGPT)
Platelets	Creatinine
Urinalysis	Ethanol testing ^{b,c}
Specific gravity	Urine drug screen ^c
pH	Hepatitis B surface antigen
Protein	Hepatitis C antibody
Glucose	HIV
Ketones	
Bilirubin	
Urobilinogen	
Blood	
Nitrite	
Microscopic examination of sediment ^a	
Coagulation	
Prothrombin time/international normalized ratio	
Activated partial thromboplastin time	

Abbreviations: HIV = human immunodeficiency virus; RBC = red blood cells; SGOT = serum glutamic oxaloacetic transaminase; SGPT = glutamic-pyruvic transaminase; WBC = white blood cells.

a Test only if dipstick result is abnormal.

b At site discretion this may be a serum, breath, or urine sample.

c Urine drug screen and ethanol level may be repeated before admission to the site.

d May not be collected in Japan.

Laboratory Tests during Study (Performed at Central/Local Laboratory)

Hematology ^a	Clinical chemistry ^a
Hematocrit	Sodium
Hemoglobin	Potassium
Erythrocyte count (RBC) ^a	Bicarbonate ^e
Mean cell volume	Uric acid
Mean cell hemoglobin	Chloride
Mean cell hemoglobin concentration	Calcium
Leukocytes (WBC)	Glucose
Cell morphology (absolute or relative % counts)	Blood urea nitrogen
Neutrophils	Total protein
Lymphocytes	Albumin
Monocytes	Total bilirubin
Eosinophils	Alkaline phosphatase
Basophils	Aspartate aminotransferase (SGOT)
Platelets	Alanine aminotransferase (SGPT)
Urinalysis ^a	Creatinine
Specific gravity	Total cholesterol
pH	Low-density lipoprotein cholesterol
Protein	High-density lipoprotein cholesterol
Glucose	Triglycerides
Ketones	Ethanol testing ^{c,d}
Bilirubin	Urine drug screen ^{c,d}
Urobilinogen	Anti-LY antibodies/immunogenicity ^h
Blood	Cerebrospinal fluid ^e
Nitrite	Glucose ^d
Microscopic examination of sediment ^b	Total protein ^d
Coagulation ^d	Blood (visual inspection) ^f
Prothrombin time/international normalized ratio ^d	WBC ^d
Activated partial thromboplastin time ^d	Exploratory immune safety laboratory tests ^g

Abbreviations: LY = LY3002813; RBC = red blood cells; SGOT = serum glutamic oxaloacetic transaminase; SGPT = glutamic-pyruvic transaminase; WBC = white blood cells.

a Results will be validated by the central laboratory at the time of initial testing.

b Test only if dipstick result is abnormal.

c May be done, as needed, at the discretion of the investigator. Ethanol testing may be done with serum, breath, or urine sample.

d Performed at local laboratory. Results will be validated by local laboratory at the time of initial testing.

e May not be collected in Japan.

f Performed at time of collection.

g If testing ordered, will be performed at central laboratory.

h Results will be validated by the central laboratory.

